4.3 Study Visits & Procedures

Study Visits:

The study procedures to be conducted for each subject enrolled in the study are presented in tabular form in Appendix 1 and described in the text that follows. Additional information is provided in the manual of operating procedures.

The study team will attempt to coordinate all of the research questionnaires and physical therapy sessions with the patient's other inpatient and outpatient appointments at VAPHS. However, if this is not possible, the patient will be required to come in for additional visits to complete the research surveys and physical tests at the described study time-points. The total additional time required for the subject participating in this research study is approximately 4-5 hours (not including transportation to and from VAPHS). Patients participation in this study will be approximately 3-4 months and will consist of 1-2

visits prior to surgery, the day of surgery visits (pre- and post- surgery), their in-hospital post-surgery visits and two follow-up visits, scheduled in conjunction with their standard of care ortho scheduled post-surgery visits.

After surgery, all patients will undergo the same standardized PT/OT best-evidence care plans (knee-specific, and hip-specific, respectively) consistent with current clinical care at VA Pittsburgh Healthcare System.

Throughout the study and after the patient signs consent, if the patient is signed up to use the VA MyHealtheVet online tool, communication between the patient and study team can occur using the secure messaging tool offered through MyHealtheVet.

Screening/Baseline Visits

The screening and baseline visit can be completed on the same day, if feasible. No research screening or baseline procedures can be conducted until informed consent is complete.

Baseline assessments will include demographics (including age and weight), smoking status, diabetes status, comorbidity (CIRS: cumulative illness rating scale), completion of research questionnaires, and completion of physical therapy procedures.

If a patient has a significant health status change after the baseline visit, but before the scheduled surgery, the study team will evaluate the patient's current medical status and determine if the health status change will affect the baseline data. In the rare occasion that the study team determines the patient's baseline data will be affected, the patient will be asked to come back to the clinic for a second baseline visit. The patient will be compensated for this visit and all baseline procedures will be repeated. As this repeated baseline visit is for data integrity only, and not for safety purposes, if the patient refuses to come back in for the repeat baseline visit, they will not be removed from the study. The study team will document this as a minor protocol deviation and the patient will continue on the study as previously planned. .

Prior to the day of surgery, the patient will complete a standard of care IMPACT visit. (IMPACT: VAPHS preoperative clinic – Interdisciplinary Medical Perioperative Assessment Consultation and Treatment).

Day of Surgery

On the day of surgery, the patient will receive anesthesia/study drug. Research questionnaires will be completed pre- and post-surgical procedure. Please refer to Appendix 1 for additional details.

In-Hospital Post-op Days (1-5)

Post-op in hospital visits will occur while the patient is in the hospital.

Follow-up visits 1 and 2

These two visits will be done in conjunction with the patient's standard of care orthopedic post-op visits.

Study Procedures:

Study Questionnaires:

Short-Form McGill Pain Questionnaire (SF-MPQ) – version 2 (Specific Aim)

The SF-MPQ questionnaire will be used to measure the subject's knee or hip pain. The questionnaire consists of 15 different qualities of pain and related symptoms, in which the subject is asked to rate the intensity of each symptom on a scale (none, mild, moderate, or severe). The questionnaire also includes two additional items relating to the patient's current pain. This questionnaire takes 5-10 minutes to complete.

SF-8 Survey

The SF-8 Health Survey is a short 8-question survey designed to measure the patient's overall health at 24-hour intervals. It takes less than 3 minutes to complete (21).

Short-Form 36 Health Survey (SF-36)

The Short Form (SF) 36 Health Survey is a 36-item, patient-reported survey of patient health at one-month intervals. The SF-36 consists of eight scaled scores, which are the weighted sums of the questions in their section. The eight sections are: vitality, physical functioning, bodily pain, general health perceptions, physical role functioning, emotional role functioning, social role functioning and mental health. The questionnaire takes approximately 5-10 minutes to complete.

QoR-15 Questionnaire:

The QoR-15 form is a 15 question survey that evaluates the quality of recovery (QoR) after anesthesia. The QoR-15 short-form questionnaire was created using extensive clinical and research experience with the 40-item QoR-40 questionnaire (with which the PI has prior research experience), and taking the strongest psychometrically-performing items from each of the five dimensions of the QoR-40 to create a short-form version (22). The QoR-15 was evaluated in 127 adult patients after general anesthesia and surgery (22). It performs well in all dimensions, and takes about 2.5 minutes to complete (22).

Opioid-Related Symptom Distress Scale (ORSDS)

The Opioid-Related Symptom Distress Scale (ORSDS) is a 4-point scale that evaluates 3 symptom distress dimensions (frequency, severity, bothersomeness) for 12 symptoms (23). The symptom-specific ORSDS is the average of the 3 symptom distress dimensions (23). The composite ORSDS is the average of 12 symptom-specific scores (23). The ORSDS is a valid tool for assessment of opioid side effects after orthopedic surgery, and can be used in clinical trials involving a wide variety of anesthetic and analgesic regimens (23).

Defense & Veterans Pain Rating Scale (DVPRS) and Supplemental Questions (DVPRS-IH, with “IH” indicating “in hospital”): The DVPRS is a graphic tool clinicians can use to facilitate self-reported pain diagnoses from patients. The DVPRS is an easy-to-use pain rating scale where the patient can rate their pain on a scale of 0-10 with 10 being the worst possible pain. The supplemental questions (DVPRS-IH) includes 4 additional questions regarding how pain over the last 24 hours has affected the patient's activity, sleep, mood, and stress. The whole questionnaire takes less than 3 minutes to complete, and will be administered at every preoperative, in-hospital, and follow-up assessment.

Western Ontario and McMaster Universities Osteoarthritis Index Physical Function Subscale (WOMAC-PF):

For patient-reported outcome of function, we will use the data generated by Western Ontario and McMaster Universities Osteoarthritis Index Physical Function Subscale (WOMAC-PF). The entire WOMAC instrument will be administered. This instrument was developed based on patient input and is the instrument of choice to assess outcome post-TKA and THA (20). The WOMAC-PF consists of 17 items related to physical function. Each item is scored on a 5-point Likert-type Scale with descriptors from 0-4 (none, mild, moderate, severe, and extreme difficulty). Scores of each item are summed for a maximum total score on the WOMAC-PF of 68. Higher scores indicate worse functional limitations. Reliability and validity of this instrument have been established (25-27). This will be given before surgery and at Follow-Up Visit 2 after surgery. Licensing rights to this questionnaire have been purchased by the study team for use in this research study.

Falls Questionnaire:

Throughout the study, the patients will be asked about their falls history. The information collected will include but is not limited to, how many falls the patient experienced in the past year (done at baseline), how many falls since the last assessment (in-hospital visits and Follow-Up Visit 2), questions regarding loss of balance, whether or not the patient is afraid of falling, and was medical treatment sought after any falls.

Clinical Assessments

None of the clinical assessments listed below are being done due to safety concerns, as such, if the physical therapist or treating physician feels that due to the patients' medical condition (such as a knee immobilizer), that some or all of the physical therapy tests cannot be completed at the specified protocol time points; the physical therapy testing will be considered optional for these patients and will be done at the discretion of the treating physician and physical therapist. If physical therapy testing is not completed due to the patient preparing for discharge and/or the patient has been discharged, this will not be considered a protocol deviation.

Gait Speed: Self-selected gait speed is measured in meters/second while subjects walk a 4 meter path located in the middle of a longer path of 9 meters to avoid acceleration or deceleration. Subjects are asked to walk at their regular pace, and time is measured with a stop watch. This test takes around 2 minutes.

Repeated Chair Stand Test: The repeated chair stand test is a simple test to assess strength of the muscles of the lower extremities and static balance. It measures the time that a person takes to stand from a chair 5 times. It takes approximately 1 minute to complete the repeated chair stand test.

Standing Balance Test:

This test is only performed on those patients who can stand unassisted without the use of a cane or walker. Moreover, the participant stands at an arm's reach of a steady surface on one side (*e.g., bed head/sideboard, grab bar*) and the tester on the other side. There are three (3) balance tests that differ by their feet position (*i.e., side-to-side, semi-tandem, and tandem*). The balance tests are performed at each assessment visit. For each:

1. The tester will ask the participant if they can stand without the device and are willing to try the test. If they reply “yes” the tester can assist them with getting into the correct position for testing.
2. The tester, for each position, will not only describe to the participant what the test is but will also demonstrate the appropriate position of the feet for testing.
3. The participant will get into the proper position while receiving support from the tester.

When the participant appears to be steady, ask if they are ready. When they reply “yes”, the tester says “Ready, begin”. The tester begins timing (i.e. starts the stopwatch) once the participant is standing independently without support from the tester. The timing for each test continues until the participant moves their feet, grabs for support, receives support from the tester or the time (10 seconds) has elapsed. This exam takes around 3 minutes.

Single Leg Balance Test:

This test will only be performed in patients who were able to complete the standing balance test. The single leg balance test is recommended to quickly assess global functional level, and its scores are related to risk for falls.

- Participants are asked to stand on one foot for 45 seconds. The other foot is raised so that the raised foot is near but not touching the ankle of their stance limb.
- The participant may use the arms, bend the knee, or move the body to maintain balance.

The tester uses a stopwatch to measure the amount of time the participant is able to stand on one limb. Time commences when the participant raises the foot off the floor. Time ends when the participant either: (1) uses the raised foot (moved it toward or away from the standing limb or touched the floor), (2) moves the weight-bearing foot to maintain his balance (ie, rotated foot on the ground), (3) a maximum of 45 seconds elapses. Three trials are performed in each side and recorded. This exam takes around 6 minutes.

Crude Sensory Examination: Sensory examination is carried out by touching lightly the patient in the specified anatomic distribution of L2-L4 and L4-S3 bilaterally, while the patient has his eyes closed. The patient is asked if the sensation is of equal intensity on both sides (normal), or if one side feels less than the other, or is unable to be felt (diminished or absent). This exam takes around 2 minutes.

Hip, Knee and Ankle Range of Motion: Range of joint movement is measured with a standard goniometer during passive (movement assisted by the tester) and active (without assistance by the tester) movements. Range of motion is tested with the subject lying in supine on the hospital bed or examination table. This is performed on both sides and recorded in degrees. Range of motion takes approximately 5 minutes.

Straight Leg Raise: The subject is asked to raise one lower extremity from the hospital bed up to approximately 45 degrees from the horizontal without bending the knee. The test is performed in both sides, and is recorded as “Yes” if the subject is able to raise the lower extremity higher than 20 degrees from the horizontal, or “No” if unable to lift the leg at that level. During this test the examiner also observes the presence of a knee extension lag, which is defined as a knee flexion (lag) equal or greater than 5 degrees during the straight leg raise. It takes approximately 3 minutes for the straight leg raise activity.

Stair climbing time: This test measures the time the subject takes to go up a flight of stairs. Subjects are instructed to use the handrail for safety purposes. The tester uses a stop watch to record time. It takes approximately 5 minutes for this test.

Functional Independence Measure (FIM): The Functional Independence Measurement (FIM) is an outcome measurement tool to assess overall independence during specific functional tasks. The FIM is composed of 18 specific tasks that are commonly assessed and treated by physical therapists, occupational therapists, nurses, and other rehabilitation professionals. FIM tasks related to transfers, walking, and stair climbing ability are all assessed in this study. Each item is scored from 1-7 based on level of independence, where 1 represents total dependence and 7 indicates complete independence. The FIM scale is used to measure the patient's progress and assess rehabilitation outcomes. It takes approximately 15 minutes for the physical therapist to administer the tests for each patient.

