2.2 Preliminary Studies

Since July 2011, our center (VA Pittsburgh Healthcare System) has routinely used MMPNA with CBD (with bupivacaine) for its peripheral nerve blocks postoperative analgesia (in addition to the intraoperative spinal anesthetic for reliable surgical anesthesia). We have since published our observed outcomes for these patients (*Pain Medicine* 2015, ref.9), which was a median analgesic duration of 37 hr (95% confidence interval of the mean being 30-49 hr).

The duration of nerve block analgesia (as opposed to “numbness” or motor block) is important since longer duration appears to attenuate patient’s “rebound pain”⁽¹¹⁾. Since CBD are “motor sparing” analgesic adjuvants to local anesthetics used in nerve blocks, CBD added to bupivacaine will help extend the duration of analgesia, but would not necessarily prolong motor block. We anticipate that higher rebound pain scores will inhibit the achievement of postoperative PT/OT objectives.

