4.0 Research Design and Methods

4.1 Type of Study

This is a single-site study that will take place at VA Pittsburgh Healthcare System, Pittsburgh, PA. It is a prospective randomized clinical trial evaluating the two different nerve block injection drugs for TKA and THA, introduced above and described further below. All described RegA techniques strategically avoid GETA and high-dose opioids, and the immediate postoperative complications (from GETA and high-dose opioids) that inhibit full-capacity cognitive function needed to accomplish PT/OT goals during the first 2 days after TKA/THA. Two hundred (200) total patients will be recruited and evaluated for study outcomes pre-TKA/THA (100 for TKA, 100 for THA). Following pre-surgical evaluation, patients will be block-randomized (stratified by [a] TKA vs. THA surgical procedure, [b] age, and [c] presence of diabetes). After surgery, all patients will undergo the same standardized PT/OT best-evidence care plans consistent with current clinical care at our institution. Evaluation of study outcomes will take place during the first two days after surgery, throughout the remainder of the hospital stay (which typically ranges from 2 to 5 days, including discharge day), and during the first two orthopedic post-op follow-up evaluations. The primary outcome is pain at 24 hr after surgery, and exploratory outcomes include physical therapy progress and anesthesia-related symptoms. We will also assess additional metrics of anesthesia and physical therapy success such as range of motion, physical function and performance testing, length of hospital stay, discharge placement, readmission, falls, and other adverse events.

Study Treatment Groups:

Institutional Standard of Care (ISOC)

All patients will receive a standardized bupivacaine spinal anesthetic, consistent with current institutional practice. All patients will receive pre-medications for the prevention of pain, nausea, vomiting, and gastroesophageal reflux, consistent with current institutional practice. All patients will receive intravenous hydration, intravenous antiemetics, and intravenous blood pressure support (e.g., intravenous phenylephrine bolus/infusion) consistent with our current institutional practice. The need for intraoperative blood transfusion will occur based on current institutional practice and collaborative decision-making between the surgical and anesthesia teams, consistent with current institutional practice.

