4.4 Data Collection

Primary Outcome – Pain

Pain - Pain will be measured by the Short-Form McGill Pain Questionnaire (36). (SF-MPQ, version 2) and the Defense and Veterans Pain Rating Scale (DVPRS, which entails a 0-10 numeric rating scale along with step-function visual cues, color-coded visual cues, and verbal descriptors of pain intensity). The specific aim is the 24-hour pain severity as measured by the SF-MPQ. The DVPRS will be used to assess (i) “rebound pain” for pain with movement, compared with baseline, during and after nerve block analgesic effects are experienced and (ii) “block duration” (11) for time interval between block placement and peak postoperative DVPRS score with movement.

Exploratory Outcomes – Physical Function, Other Symptoms, and Recovery from Anesthesia

Data will be recorded by the research coordinator and/or VAPHS Staff Physical Therapists and/or “without compensation” (WOC) physical therapists hired through the University of Pittsburgh specifically for the care of study patients.

Data Management System

Data management will be coordinated at VAPHS by StatCore. Data entry will be primarily performed using the VA’s REDCap software (https://vhacdweb05.vha.med.va.gov/redcap_v6.0.27/index.php?pid=1440) via laptop or desktop personal computers. Data will never reside on the data collection devices, which serve only as portals to the password protected database. Only authorized members of the study team will have access. Data will reside on the VA Informatics & Computing Infrastructure (VINCI) server – which is also password protected and independent from all other servers. Data will be downloaded from the REDCap server by StatCore for analytic and data management purposes. Downloaded data will reside on a password-protected VAPHS secure shared drive. REDCap is a secure web-based platform that can only be accessed through the VA intranet, and it is situated behind the VA firewall. Account login information is required, and then the data are stored on the REDCap server. The data to be entered (and catalogued in a detailed data dictionary) are password-protected within REDCap via login requirements, and the downloaded data are secured by permission only access to the shared drive (\\\whapthshare\Nerve_Block_Study\).

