5.6 Sample Size Determination

Although the SF-MPQ data is the basis of our specific aim, we do not have our own preliminary SF-MPQ data. So we will base our sample size on our most robust data, that being nerve block duration from our observational data (40 hr mean, with 14 hr standard deviation). Hip replacement and knee replacement surgery are different procedures requiring anatomically different nerve blocks as described above, so we will consider these samples as separate. We consider a doubling of the nerve block duration (15 hr for plain bupivacaine, 30 hr for bupivacaine-CBD) as a clinically significant difference with respect to the military objectives of evacuation and transport. We forecast that as a single-drug (and based on historical literature), the standard deviation of plain bupivacaine duration would be half of the 15 hr projected duration (i.e., 7.5 hr). Due to likely variability in study participant responsiveness to the 4-drug mixture, we predict that the standard deviation of the bupivacaine-CBD treatment would also be half of the projected 30 hr duration (i.e., 15 hr). We believe that the 30 (SD=15) hr duration for bupivacaine-CBD is a reasonably conservative duration based on our preliminary data of 40 (14) hr block duration. Using a 2-tailed t-test with $\alpha=0.05$, 20 patients per procedure for bupivacaine treatment, and 80 patients per bupivacaine-CBD treatment would yield 95% statistical power. This sample size will also accommodate for our multiple secondary aims. Attrition of 6 active control treatment patients ($n=14$) and of 24 MMPNA-treated patients ($n=56$) will still yield just over 80% statistical power. All calculations were performed using IBM SPSS SamplePower version 3.0.1, Chicago, IL.

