APPENDIX 1: Study Calendar

	Screening Visit ^a	Baseline Visit	Day of surgery		Post-Op Day 1	Post-Op Day 2	Post-Op Day 3	Post-Op Day 4	Post-Op Day 5	Follow-Up Visit 1 ^d	Follow-Up Visit 2 ^{c, e}
			Pre-Procedure	Post-Procedure							
Clinical Assessments											
Informed Consent	X										
Determine Eligibility	X										
Demographics	X										
Orthopedic & IMPACT evaluation		X									
Crude Sensation in L2-L4 & L4-S3		X			X	X	X	X	X		X
Straight Leg Raise & Range of Motion		X			X	X	X	X	X		X
Functional Independent Measure (FIM)		X			X	X	X	X	X		X
Standing Balance Test		X			X	X	X	X	X		X
Single Leg Balance Test ^g		X									X
Gait Speed		X			X	X	X	X	X		X
Repeated Chair Stand Test		X				X	X	X	X		X
Stair Climbing Time		X									X
Physical Therapy/ Therapeutic Exercises					X	X	X	X	X		
Comorbidity (CIRS)		X									
Interim Changes											X
Discharge Disposition											X
Opioid Consumption					X ^g						
Anesthesia/Study Drugs			X								
Adverse Events		X	X	X	X	X					
Concomitant Medications		X	X	X	X	X					

	Screening Visit	Baseline Visit	Day of surgery		Post-Op Day 1	Post-Op Day 2	Post-Op Day 3	Post-Op Day 4	Post-Op Day 5	Follow-Up Visit 1	Follow-Up Visit 2 ^{c, e}
			Pre-Procedure	Post-procedure							
Questionnaires											
SFMPQ-2 ^b		X	X	X	X	X	X	X	X		X
DVPRS		X	X	X						X	X
DVPRS- in hospital ^b					X	X	X	X	X		
ORSDS ^b		X			X	X	X	X	X		
QOR-15 ^b		X			X	X	X	X	X		X
WOMAC		X									X
SF-8 ^b			X		X	X	X	X	X	X	
SF-36		X									X
Falls Questionnaire		X			X	X	X	X	X		X

a. The screening visit and baseline visit can be completed on the same day.

b. On post-op hospital days and post-op week 6 follow-up visits, these questionnaires will be completed before the subject has their first physical therapy session for the day.

c. If a patient decides to withdraw from the study after having their surgery, or is withdrawn by the study team during or after their surgery, they will be asked to complete Follow-Up Visit 2.

d. Follow-up visit 1 will occur with the patient's already scheduled standard of care follow-up orthopedic visits. Follow-Up Visit 1 may be performed as a phone call if necessary.

e. Follow up visit 2 will be scheduled to coincide with the patient's standard of care follow-up orthopedic visits.

f. Patient must pass the standing balance test first, before the single leg balance test can be attempted.

g. Opioid consumption will stop being collected at the time of the patient's discharge.

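### In patients discharged by about 48 h, the pain and opioid record can end before a 4-drug block wears off but not before a plain block does, which distorts rebound pain, block duration and opioid totals (not the 24 h primary outcome).

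*Combined protocol and SAP*

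**What the plan says.** Under the Post-Op Days 1-5 heading, section 4.3 states that "Post-op in hospital visits will occur while the patient is in the hospital". The calendar in Appendix 1 places the daily SF-MPQ-2, in-hospital DVPRS and ORSDS on those days. Footnote g adds: "Opioid consumption will stop being collected at the time of the patient's discharge". The calendar's concomitant-medication row ends at Post-Op Day 2.

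After discharge, the next pain record is the DVPRS at Follow-Up Visit 1. The orthopedic clinic sets its date, and it may be a phone call. Appendix 2 (Amendment 6) shows that it used to be called the 2-week visit. SF-MPQ-2 returns at Follow-Up Visit 2.

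Section 4.4 uses DVPRS for two derived measures. Rebound pain is assessed "for pain with movement, compared with baseline, during and after nerve block analgesic effects are experienced". Block duration runs from placement of the block to the highest postoperative score on movement.

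On length of stay, section 4.1 gives only "the hospital stay (which typically ranges from 2 to 5 days, including discharge day". Section 5.6 plans on 15 h (SD 7.5) for plain bupivacaine and 30 h (SD 15) for the 4-drug block, and calls the latter "a reasonably conservative duration based on our preliminary data of 40 (14) hr block duration".

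**The concern.** Both derived measures need the period after the block has worn off. With plain bupivacaine that period falls in hospital for practically any patient who stays two days. With the 4-drug block it may fall at home, where nothing is scheduled until the follow-up visit.

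A patient who goes home with the block still working has no recorded rebound peak. The highest available score is then either an inpatient score from before the rebound or one taken at a follow-up visit long after it. Neither is the quantity section 4.4 describes. Deleting observations with missing values (section 5.1) does not help, because such a patient still has inpatient scores and therefore a maximum.

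The direction of the error depends on the measure. A missed peak flatters the 4-drug block on rebound pain. Taking an inpatient score as the peak shortens its measured duration. For opioids, a total that stops at discharge covers more time after the block in controls. What is at stake is whether the trial can separate a block that reduces rebound pain from one that delays it past discharge. That matters because section 1.0 looks ahead to possible adoption of the 4-drug block in general practice.

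**Working it through.** **The plan's own tail figure.** Section 5.2 takes a mean of 48 h and an SD of 14 h and states that 97.5% of blocks have resolved by 76 h. Under a normal distribution, Φ((76 − 48)/14) = Φ(2.0) = 97.7%, so the figure is reproduced up to rounding. The same calculation is used below.

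**Inputs.** Section 5.6 gives plain 15 h (SD 7.5), 4-drug planning value 30 h (SD 15) and 4-drug observational value 40 h (SD 14). Hours are counted from block placement. Discharge time is taken as independent of arm and of block status.

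**Share still working at the last inpatient record at time t** = 1 − Φ((t − mean)/SD).

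| Last record | Plain 15/7.5 | 4-drug 30/15 | 4-drug 40/14 |
|---|---|---|---|
| 48 h | z = 33/7.5 = 4.40; about 0.001% | z = 18/15 = 1.20; 11.5% | z = 8/14 = 0.57; 28.4% |
| 72 h | z = 57/7.5 = 7.60; about 0% | z = 42/15 = 2.80; 0.3% | z = 32/14 = 2.29; 1.1% |
| 96 h | about 0% | z = 66/15 = 4.40; below 0.01% | z = 56/14 = 4.00; below 0.01% |

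**Sensitivity.** A lognormal with the same means and SDs gives 11-24% against 0.35% at 48 h, 1.8-2.9% against 0.02% at 72 h, and about 0.3% against practically 0% at 96 h. With the 48 h mean that section 5.2 treats as conservative (normal, SD 14), 50% of 4-drug blocks are still working at 48 h and 4.3% at 72 h.

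**In patients.** If every last record were at 48 h, 160 × 0.115 ≈ 18 to 160 × 0.284 ≈ 45 of the 160 4-drug patients would leave before the block ended, and 0 of the 40 controls. These are ceilings for a 48 h discharge. The real number is this multiplied by the share who leave that early, which the documents do not give.

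**Opioid totals to discharge.** At the mean durations, a 48 h stay contains 48 − 15 = 33 h after the block in controls, and 48 − 30 = 18 h or 48 − 40 = 8 h in the 4-drug arm.

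**The case against.** The strongest reply is that exposure is unknown and may be small. Two days is the lower end of a 2-5 day range, and no distribution is given. Section 5.2 expects that a patient still numb at 72-76 h would probably be an inpatient, and by 72 h the problem has nearly gone. Section 1.0 frames the outcomes beyond the specific aim as exploratory. This stands, and it limits the severity.

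A second reply is that other text could recover the data. Section 4.3 allows additional visits for surveys at study time points, and section 5.2 lists dated questions about the first oral and intravenous opioid doses that did not help. The extra visits are not tied to Post-Op Days 1-5, which are explicitly inpatient. The section 5.2 questions have no assigned visit and would date the end of analgesia without giving a peak score. Section 4.4 does not say that only inpatient scores count towards the peak, but no other DVPRS score is scheduled near the time of rebound. The manual of operating procedures may say more and is not available here.

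Several stronger readings are tempting, and the documents do not support them:

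- Pain recording stops for good at discharge. It is interrupted: DVPRS returns at both follow-up visits.
- Discharge is often around Day 2. Nothing in the documents says how often.
- Opioid need after the block is lost almost only in the 4-drug arm. Home use is unrecorded in both arms, and for a control discharged at 48 h it is all post-block use. The imbalance lies in how much post-block time the recorded total covers.
- Most 4-drug blocks outlast the record. At a last record of 24 h the shares would be 66-87%, but section 4.1 plans evaluation over the first two days after surgery, and 11.5% of plain blocks would then still be working too.
- The bias can be put in pain-score points. That needs a size of rebound and a share of early discharges, and the documents give neither.

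**Conclusion.** The concern holds for patients discharged by about 48 h. On the plan's own durations, about 12-28% of 4-drug blocks and about 0% of plain blocks would outlast the inpatient record in these patients. Peak rebound pain is then understated and block duration shortened almost only in the 4-drug arm, and opioid totals to discharge cover unequal post-block time. For discharge at 72 h the share is about 0.3-1.1%.

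The 24 h SF-MPQ-2 primary outcome is not affected. The size of the bias across the whole trial cannot be derived from the documents. The percentages rest on normal durations (a lognormal changes them little at 48 h) and on discharge being unrelated to block status. The latter could fail in either direction: section 5.1 counts return home among the outcomes the block may improve, while section 2.1 expects lingering numbness to delay therapy. Severity is minor to moderate, for secondary and exploratory outcomes only.

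**What to change.** 1. At Follow-Up Visit 1, which already records DVPRS and may be by phone, ask for the worst pain with movement since discharge, its date and approximate time, and the number of opioid tablets taken in the first days at home.
2. In the analysis plan, treat a patient discharged before block offset or rebound as right-censored for block duration at the last inpatient record. Do not use the highest inpatient score as that patient's peak. Fix in advance, before unblinding, how an observed rebound is recognised, and report the number censored in each arm. The recalled time can serve as a supporting analysis.
3. Compare peak pain and opioid totals over one fixed window from block placement in both arms, not to discharge. A window of 96 h leaves below 0.01% of 4-drug blocks unresolved under the normal model and about 0.3% under the lognormal. For a patient discharged at 48 h it requires 96 − 48 = 48 h of recalled home data.

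The cost is a few questions at an existing contact and some analysis wording. The downside is recall error, since the clinic sets the visit date and it may be about two weeks after surgery. Right-censoring also assumes that discharge is unrelated to how much longer the block would have lasted, and this should be stated with the result.
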